2.1 Background and Rationale

Uncontrolled hypertension in young adults is an enormous public health burden.^{1,2} In the U.S., over 10 million 18-39 year-olds (1 in 5 men; 1 in 6 women) have hypertension,³⁻⁶ increasing their risk of heart failure, stroke, and chronic kidney disease.^{5,7-10} The medical costs of hypertension and its complications are \$131 billion/year,^{11,12} contributing to 1,000 deaths per day.^{3,5,11,13-15} Young adults with hypertension have a higher lifetime risk for cardiovascular disease, especially with complicated hypertension (hypertension with diabetes or chronic kidney disease).^{9,14-20} Hypertension control reduces morbidity, mortality, and future healthcare costs,²¹⁻²⁵ yet, only 35% of young adults with hypertension in the U.S. have achieved blood pressure control (blood pressure <140/90 mmHg).²⁶⁻²⁹

While hypertension self-management programs targeted towards adults ≥ 50 years old reduce blood pressure,³⁰⁻⁴⁸ they primarily focus on medication titration.⁴⁹ In contrast, a trial of lifestyle modifications is commonly the initial hypertension treatment step, rather than a medication, among young adults.⁵⁰ Medication initiation is also not enough to achieve long-term blood pressure control in young adults. Even with medication adherence, systolic blood pressure continues to increase from younger to older age.⁵¹ Therefore, young adults need additional hypertension self-management (home blood pressure monitoring and lifestyle modifications) to lower blood pressures and reduce the amount of medication they may need over a lifetime.⁵²⁻⁵⁵

The Institute of Medicine⁵⁶ highlighted the importance of self-management support to learn and effectively perform self-management.^{30,34,36,57,58} In multiple studies among older adults, hypertension self-management is superior to office-based management.^{30,34,36,57-59} However, in contrast to older adults, young adulthood is a time of frequent healthcare and vocational transitions, new life responsibilities, and less interest in health-related goals (*i.e.*, prevention of heart attack and stroke).^{60,61} Thus, the content and method of delivery of hypertension self-management must be individualized to young adults and address barriers specific to this population.⁶²⁻⁶⁴

Our previous research highlighted the critical need to design hypertension programs targeted at young adults. An analysis of 48 months of data ([name], et al.), published in the *Journal of Hypertension*,⁶⁰ evaluated diagnosis rates of 4,023 young adults with regular primary care visits and ongoing elevated blood pressures, but without a hypertension diagnosis. Among adults (≥ 18 years) only ~59% of young adults (18-39 year-olds) received an initial hypertension diagnosis as compared to over 70% of ≥ 40 year-olds ($p < 0.001$). After adjustment for patient comorbidities, sociodemographic, and provider characteristics, young adults had a 33% lower rate of receiving a hypertension diagnosis compared to ≥ 60 year-olds ($p = 0.007$). In a separate study, we demonstrated that young adults with isolated systolic hypertension had a 50% slower diagnosis rate than young adults with isolated diastolic or combined systolic/diastolic hypertension ($p < 0.001$).⁶⁵ Our publication in the *Journal of General Internal Medicine*⁵⁰ demonstrated similar disparities in hypertension treatment. Adjusted analysis demonstrated that young adults had a 44% lower rate of medication initiation (HR 0.56; 0.47-0.67, $p < 0.001$) than ≥ 60 year-olds. Thus, many more young adults continued on with uncontrolled blood pressure and no medication.

We also published the first U.S. analysis describing electronic health record documentation of lifestyle education for young adults with incident (new) hypertension ([name], et al.).⁶⁶ Among 500 randomly selected 18-39 year-olds, only 55% had documented lifestyle education within one year of developing hypertension. Critical provider and patient barriers included limited time to manage multiple co-morbidities and clinic visit non-adherence (no-shows, not scheduling follow-up visits), respectively. Therefore, out-of-clinic self-management support is needed to overcome these barriers. Of note, there were not significant race/ethnicity differences despite the higher prevalence of hypertension among Black young adults.⁶⁷

2.1.1 Development of MyHEART

To address the unmet need in hypertensive care for young adults, we developed MyHEART (My Hypertension Education And Reaching Target), a multi-component, theoretically-based intervention designed to achieve self-management among young adults with uncontrolled hypertension. MyHEART is a patient-centered program that uses evidence-based health behavior approaches to lower blood pressure. MyHEART differs from previous interventions by: **1)** targeting barriers identified by young adults in our preliminary research, **2)** tailoring the mode of delivery to preferences expressed by members of this age group, and **3)** individualizing action plans to participants' motivations and behavior goals. To design this intervention, we conducted focus groups of young adults with hypertension (45%

Black)⁶¹ and one-on-one interviews of providers⁶⁸ in Madison (academic community), Milwaukee (urban), and Richland Center (rural), Wisconsin. Our diverse young adult respondents expressed a strong interest in blood pressure self-monitoring and increased communication with their healthcare team. They helped us recognize important hypertension education topics that were not addressed in current healthcare system handouts. Stakeholders identified barriers to hypertension self-management and hypertension control among young adults, justifying the need for this intervention, and proposed specific solutions to the identified barriers.

MyHEART is founded on the Self-Determination Theory (SDT), which is used to support chronic disease self-management and lifestyle modifications.⁶⁹⁻⁷³ SDT has been used across races/ethnicities and with young adults.^{74,75} To reduce the risk of negative sequelae from long-term hypertension, we need to not only initiate behaviors for blood pressure control, but also foster maintenance of new behaviors. SDT acknowledges that young adults are more likely to adopt and maintain health behaviors with: **1**) autonomous (internal) motivation, instead of external motivation (i.e., external pressure), **2**) relatedness (i.e., supportive healthcare interactions), and **3**) perceived self-competence (i.e., perceived self-efficacy;^{76,77} confidence in starting and maintaining behaviors to reach a goal).^{69,72,74,78-89} The information gained by applying a theoretical framework is crucial to designing interventions and understanding the translation of interventions to other chronic diseases and populations.⁹⁰

MyHEART incorporates important hypertension education components implemented by a health coach: **1**) telephone-based self-management counseling, **2**) home blood pressure monitoring, and **3**) young adult-focused hypertension education. These components are recommended by the Institute of Medicine⁹¹ and the American Heart Association;¹ in previous studies, the largest effect sizes were achieved by multi-component interventions that incorporated both behavioral and educational strategies.^{92,93} Health coaching provides informational and emotional support for chronic disease management.⁹⁴⁻⁹⁶ Telephone interventions increase contacts between patients and their healthcare team.⁹⁷⁻¹⁰⁰ MyHEART uses telephone as the primary mode of communication between participants and coaches, because young adults indicated a preference for this mode of delivery. Contrary to our hypothesis, our focus group respondents disliked text messaging and social media for health coach communication or self-management reminders;⁶¹ young adults were concerned that peers would see the hypertension communications.

MyHEART directly addresses NHLBI's Strategic Priority 3.1.a to: "Develop and evaluate new approaches to implement proven preventive and lifestyle interventions." MyHEART takes guideline-recommended hypertension self-management tools and, in contrast to previous interventions, targets the delivery to young adults to increase the initiation and maintenance of behaviors to lower blood pressure.

2.2 Hypothesis

Aim 1. To evaluate the effect of MyHEART (home blood pressure monitor distribution and health coaching) on clinical outcomes, the change in systolic and diastolic blood pressure (primary) and hypertension control (secondary) after 6 and 12 months, compared to usual clinical care. **We hypothesize** that MyHEART will significantly decrease systolic and diastolic blood pressures (clinic and 24-hour ambulatory) in young adults, compared to usual clinical care.

Aim 2. To evaluate the effect of MyHEART on hypertension self-management behavior (behavioral outcomes) at 6 and 12 months, compared to usual clinical care. **We hypothesize** that MyHEART will increase the frequency of home blood pressure monitoring and lifestyle modifications (increased physical activity, decreased sodium intake).

Aim 3. To examine whether MyHEART's effects on self-management behavior are mediated through variables of perceived competence, autonomy, motivation, and activation (mediation outcomes). Based on our pilot study and theoretical framework, **we hypothesize** that MyHEART's effects will be mediated through perceived competence, autonomy, internal motivation, and patient activation.

2.3 Study Agent

No investigational drugs, devices, or biologics will be used in this study.

2.4 Summary of Clinical Data

Established Recommendations for Lifestyle Modifications¹⁰¹

The Fifth Report of the Joint National Committee on the Detection, Evaluation and Treatment of High Blood Pressure (JNC V) and the Working Group Report on Primary Prevention of Hypertension recommended four lifestyle modifications to reduce blood pressure: **1) reduced sodium intake, 2) weight loss, 3) reduced alcohol consumption, and 4) increased physical activity.**¹⁰² Based on the results of the Dietary Approaches to Stop Hypertension (DASH) clinical trial,¹³ the Sixth Report of the Joint National Committee also recommends a diet rich in fruits, vegetables, and low-fat dairy products, and reduced in saturated fat, total fat, and cholesterol.¹⁰³

Reduced Sodium Intake

Inter-population and intra-population observational studies have documented a positive, direct relationship between sodium intake and blood pressure, and experimental studies confirm this relationship.¹⁰⁴⁻¹⁰⁷ Furthermore, from a population perspective, the benefits of a reduced sodium diet significantly outweigh possible risks. Since most adult Americans consume well over the maximum recommended daily intake of 2,300 mg of sodium, virtually all Americans are candidates for reducing sodium intake. Trials have demonstrated that behavior change interventions can reduce daily intake by approximately 690-1150 mg.¹⁰⁸ Results tend to differ by race-ethnicity and to a lesser extent by gender, such that sodium reduction is less in African Americans than in European Americans and less in women than in men; the latter is largely explained by lower baseline intakes of sodium.¹⁰⁹ Additional analyses of data indicate a dose response relationship between sodium reduction and the extent of blood pressure reduction and hypertension control.¹³ Trials have also documented that a reduced sodium intake, once achieved, tends to be well maintained.¹¹⁰

Weight Loss

A strong and persuasive body of evidence from both observational and experimental studies indicates that weight is positively (directly) associated with blood pressure and hypertension.¹¹¹ The relationship is present in both genders and in most ethnic-racial groups. The importance of this relationship is reinforced by the high and increasing prevalence of obesity in the United States.¹¹² Virtually every major trial that has examined the influence of weight loss on blood pressure has documented a substantial and significant relationship between change in weight and change in blood pressure. Reductions in blood pressure occur even before (and without) attainment of desirable body weight. In studies that aggregated results across weight loss trials, the average SBP/DBP reduction per kg of weight loss was 1.6/1.1 mmHg.

Regular Physical Activity

Evidence from observational studies and experimental studies suggests that increased physical activity can lower blood pressure. Numerous studies have found a negative correlation between habitual physical activity and the development of hypertension. An inverse relationship between physical activity and blood pressure has been observed in both sexes, all age groups, and in both African American and European Americans.^{113,114} In addition to the observational evidence, more than 30 experimental studies have evaluated the impact of physical activity on blood pressure.^{115,116} Most of these studies used aerobic training protocols at vigorous intensities (*i.e.*, 60% maximal oxygen uptake or 70% maximal heart rate or greater). Fewer trials have evaluated lower intensity of exercise for blood pressure effects. Moderate-intensity activity has been shown to decrease blood pressure to an extent similar to, if not greater than, higher-intensity exercise in normotensive and hypertensive individuals.¹¹⁷ The entirety of these studies indicates that regular, moderate to vigorous physical activity lowers blood pressure by 10/8 mmHg in hypertensives and 2/3 mmHg in normotensives. Policy-making bodies deem the evidence sufficient to advocate regular aerobic physical activity as a means to reduce blood pressure.^{21,103,117}

Limitation of Alcohol Intake

The relationship between high alcohol intake (typically three or more drinks per day) and elevated blood pressure has been reported in a large number of observational studies.^{118,119} In the Prevention and Treatment of Hypertension Study (PATHS), a reduction in alcohol intake among moderate drinkers also reduced blood pressure to a small, albeit

nonsignificant, extent.¹²⁰ A few trials have also demonstrated that reductions in alcohol intake among heavy drinkers can lower blood pressure in normotensive and hypertensive men.^{121,122}

Dietary Patterns and Blood Pressure

Results from the Dietary Approaches to Stop Hypertension (DASH) clinical trial, in conjunction with previous studies of vegetarian diets, provide strong and persuasive evidence that modification of dietary patterns can have a profound influence on blood pressure.¹⁰⁷

2.5 Potential Risk and Benefits to Subjects

2.5.1 Known Potential Risks

Blood Pressure Cuffs: There is a small immediate risk that there may be minor discomfort or bruising at the site of the upper arm automatic blood pressure cuff. To avoid this, patients will receive the appropriately sized cuff based on their upper arm circumference. In addition, the 24-hour ambulatory monitor will be started prior to leaving the research clinic to obtain at least two blood pressures to ensure comfort. Participants will also review information on how to contact the research staff in case additional questions, concerns, or new discomfort arise.

Muscle/Joint Discomfort: There is a small immediate risk that participants may experience new muscle and/or joint discomfort after starting a new exercise program. However, they will be instructed to consult their provider before starting a new exercise program.

Questionnaires: Multiple interviewer-administered and computer-administered questionnaires and surveys will be completed at each visit. We expect this will pose very minimal risk of physical or psychological discomfort.¹²³

Breach of Confidentiality: The major potential social and psychological risk to participants is loss of confidentiality. As our standard operating procedure, we have policies and procedures in place to protect the confidentiality and security of subject data, see below in "Protection Against Risks". Young adults may be concerned about social stigma associated with high blood pressure; therefore, immediate and/or long-range psychological risk is possible. However, to minimize this risk as much as possible we will protect the confidentiality of participants with a unique subject identifier number as outlined below in "Protection Against Risks". We anticipate no additional psychological or legal consequence from study participation. Participants and their insurance plans will not be charged for any of the visits, telephone contacts, or 24-hour ambulatory blood pressure monitoring.

Reproductive risk: No reproductive risks are expected from this trial. This study does not start, change, or alter medications in any way. Patients are excluded if pregnant and if planning to become pregnant.

Hyperkalemia: The DASH diet may include a higher intake of potassium (due to a high content of daily fruits and vegetables).

Hypoglycemia: During or immediately after exercise, there is a risk of hypoglycemia for subjects with diabetes mellitus.

Clinically Significant Blood Pressure Findings: Clinically relevant results of blood pressure measurements will be released to all subjects, as well as to their specific provider if they opt to give the provider's information on the written consent form. Only clinically significant findings will be disclosed: research clinic blood pressure $\geq 160/100$ mmHg (during any research clinic visit), right/left arm blood pressure differential of ≥ 20 mmHg (Visit 1), and normal mean 24-hour ambulatory blood pressure (Visit 2). These clinical significant findings will be noted immediately during the research clinic visit, and the research examiner will notify the subject verbally, complete the incidental finding form, and provide a completed copy to the subject during the same visit. A copy of the incidental finding form will be forwarded to the primary care provider (via fax) on the same day.

The protocol appendix has a table explaining recommended primary care follow-up based upon the research clinic blood pressures (for all subjects). This is separate from the incidental finding process. Since young adults will be arriving with elevated blood pressures, they should also continue to have routine clinical care per hypertension guideline recommendations. This recommendation will be given by the research examiner on the same day as the visit.

The same primary care follow-up (protocol appendix) will also be recommended based upon home blood pressure readings (intervention arm only) by the health coach before the end of that call. However, instead of the participant being "escorted" to the emergency department, they will be instructed to call 911.

Clinically significant findings could result in anxiety and psychological discomfort. Financial risks to clinically significant findings could mean that subjects and their insurance would have to pay for follow-up procedures or visits. False-positives are possible (*i.e.*, a clinically concerning blood pressure measurement in our research clinic), that is "white coat hypertension", not high blood pressure.

An additional risk is social stigma associated with high blood pressure and associated immediate and/or long-range psychological risks.

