Adverse Event Reporting Period: Adverse events must be reported once the subject undergoes any study procedures, and adverse events must be reported during the entire active study period and for 30 days following the last administration of study treatment.

Withdrawal of subjects: Any subject who experiences an adverse event or serious adverse event will be immediately withdrawn from the study. All subjects have the option to withdraw from the study at any time. Subjects will also be immediately withdrawn from the study if they report being pregnant, planning to become pregnant, or develop a medical condition (even if unrelated from this study) that prevents them from ongoing participation in the study.

Post-study Adverse Event: All unresolved adverse events will be followed by the investigator until the events are resolved, the subject is lost to follow-up, or the adverse event is otherwise explained. At the last scheduled visit, the investigator will instruct each subject to report any subsequent event(s) that the subject, or the subject's personal physician, believes might be related to participation in this study. The investigator should notify the study sponsor, DMC, and IRB of any serious adverse event or death occurring up to 30 days after the subject has discontinued or terminated study participation that may be related to this study.

Hospitalization, Prolonged Hospitalization, or Surgery: Any adverse event that results in hospitalization or prolonged hospitalization will be documented and reported as a serious adverse event unless specifically instructed otherwise in this protocol. Any condition responsible for surgery should be documented as an adverse event if the condition meets the criteria for an adverse event.

Neither the condition, hospitalization, prolonged hospitalization, nor surgery are reported as an adverse event in the following circumstance: Hospitalization or prolonged hospitalization for diagnostic or elective surgical procedures for a preexisting condition. Surgery should **not** be reported as an outcome of an adverse event if the purpose of the surgery was elective or diagnostic and the outcome was uneventful.

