5.1 Prior and Concomitant Therapy

All concomitant antihypertensive medications prescribed by the patient's healthcare team are permitted during the study. Ongoing antihypertensive medication changes by the patient's healthcare team (including medication initiation, discontinuation, and/or dose changes) are allowed throughout the study.

All other medications, supplements, and lifestyle modifications that were part of the participant's treatment plan prior to the study are included.

The participant may also be started on non-pharmacologic therapy (examples: physical activity, stress management) by their medical team during this study.

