5.3 Established Standard of Care

Usual care and intervention arm participants will receive routine hypertension clinical care per their primary care provider. This includes the possibility of receiving untailored self-management resources (i.e., dietitian referral) at their provider's discretion, but this is not systematically tailored to young adults' needs. These patients would be treated according to current hypertension guideline standards including, but not limited to, hypertension lifestyle modification counseling: 1) reduced sodium intake, 2) weight loss, 3) reduced alcohol consumption, and 4) increased physical activity. This may include verbal discussions and/or handouts. Medications would be initiated and/or titrated per hypertension guidelines.

All patients would have clinic blood pressure checks and would be encouraged to have home blood pressure monitoring. Additionally, providers may order 24-hour Ambulatory Blood Pressure Monitoring, per the U.S. Preventive Services Task Force guidelines, to exclude white coat hypertension. Patients would also have additional tests not limited to blood draws, EKGs, echocardiograms, etc.

We will assess the number of healthcare team contacts in the usual care arm by calculating the number of primary care and specialty visits and dietitian and exercise referrals after study enrollment (see IRB application with data variable sheet).^{50,60} Usual care arm participants will receive AHA's "What is High Blood Pressure"¹³¹ handout (copies of handouts are in the Appendix).¹³² It is usual care for patients to receive hypertension educational material when presenting for a hypertension visit. They will not receive home blood pressure monitors. Usual care participants will have the same 6- and 12-month assessments as the intervention arm.

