8.1 Specifications of Safety Parameters

8.1.1 Definition of Adverse Events (AE)

An *adverse event* (AE) is any symptom, sign, illness, or experience that develops or worsens in severity during the course of the study. Intercurrent illnesses or injuries should be regarded as adverse events. Abnormal results of diagnostic procedures are considered to be adverse events if the abnormality:

- results in study withdrawal
- is associated with a serious adverse event
- is associated with clinical signs or symptoms
- leads to additional treatment or to further diagnostic tests
- is considered by the investigator to be of clinical significance

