8.3 Time Period and Frequency for Event Assessment and Follow-Up

The occurrence of an AE or SAE may come to the attention of study personnel during study visits and interviews of a study participant presenting for medical care, or upon review by a study monitor. All AEs including local and systemic reactions not meeting the criteria for SAEs will be captured on the appropriate CRF. Information to be collected includes event description, time of onset, clinician’s assessment of severity, relationship to study product (assessed only by those with the training and authority to make a diagnosis), and time of resolution/stabilization of the event. All

AEs occurring while on study must be documented appropriately regardless of relationship. All AEs will be followed to adequate resolution.

Any medical condition that is present at the time that the participant is screened will be considered as baseline and not reported as an AE. However, if the study participant's condition deteriorates at any time during the study, it will be recorded as an AE. UPs will be recorded in the data collection system throughout the study.

Changes in the severity of an AE will be documented to allow an assessment of the duration of the event at each level of severity to be performed. AEs characterized as intermittent require documentation of onset and duration of each episode.

The PI will record all reportable events with start dates occurring any time after informed consent is obtained until 30 days (for non-serious AEs and SAEs) after the last day of study participation. At each study visit, the investigator will inquire about the occurrence of AE/SAEs since the last visit. Events will be followed for outcome information until resolution or stabilization. Breaches of confidentiality and emotional upset will be reported to the PI who will then review the incident with the study staff, information technology groups, and follow-up with the participant. The PI is responsible for making the reports to the DSBM, IRB and NHLBI.

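### The disclosure list in 2.5.1 has no trigger for a severely raised 24-hour mean, so a severe result at Visit 2 or Visit 4 with clinic pressure below 160/100 prompts no stated notice

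*Combined protocol and SAP*

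**What the plan says.** Section 2.5.1 opens by promising release of clinically relevant pressure results to all subjects, and to the provider where the participant has chosen to give the provider's details. It then narrows this: "Only clinically significant findings will be disclosed". Three findings follow:

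- research clinic pressure at or above 160/100 mmHg at any visit;
- a between-arm difference of 20 mmHg or more at Visit 1;
- "and normal mean 24-hour ambulatory blood pressure (Visit 2").

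A listed finding brings verbal notice, a completed incidental finding form and a same-day fax to primary care.

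A separate appendix table of recommended follow-up is described in 2.5.1 as keyed to research clinic pressures. The same follow-up "will also be recommended based upon home blood pressure readings (intervention arm only) by the health coach".

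The other relevant places are:

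- **5.4.1.1:** at Visit 2 a staff member evaluates the 24-hour mean. The only stated consequence is exclusion and a letter for white coat hypertension. Remaining eligible patients are enrolled and randomized.
- **5.4.1.2:** participants in both arms receive copies of their clinic pressures and follow-up instructions.
- **5.4.3:** Visit 4 consists of monitor removal and payment.
- **5.4.5:** at the 12-month visit participants are told their final weight, clinic and 24-hour pressures and body mass index.
- **5.3:** for usual care, "All patients would have clinic blood pressure checks and would be encouraged to have home blood pressure monitoring", but the study supplies no monitor to that arm.

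**The concern.** A clinic reading of 160/100 gets same-day action. An equally worrying 24-hour mean gets none, although 5.2 treats ambulatory monitoring as the reference measure and 2.5.1 itself warns that clinic readings can be false positives. The study already holds the information: the Visit 2 mean is read before randomization, and under 7.2.1 ambulatory summaries go to REDCap.

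What is at stake is participant safety. Someone with a severe 24-hour mean and an unremarkable clinic reading receives follow-up advice keyed to the lower number. Coached participants have a partial safety net through home readings discussed with the coach for six months. Usual-care participants have only whatever home monitoring they arrange themselves.

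**Working it through.** **1. Which recordings lead to a notice.** The plan gives no figure to reproduce here, so the first step sets the sections side by side.

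| Recording | Stated review | Stated action if normal | Stated action if severely raised |
|---|---|---|---|
| Visit 2 (baseline) | Yes, 5.4.1.1 | Exclusion and letter | None |
| Visit 4 (6 months) | None listed in 5.4.3 | None | None |
| 12 months | Final value told to participant, 5.4.5 | None | None beyond being told |

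No clinic pressure is listed at Visit 4, so the clinic trigger at 6 months rests on Visit 3 alone.

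**2. What counts as severe.** The plan sets no upper ambulatory level. Section 3.1.2 pairs ambulatory <130/80 with clinic <140/90, an offset of 10/10 mmHg. If that offset held at higher pressures (an assumption), the counterpart of clinic 160/100 would be 160 - 10 = 150 systolic and 100 - 10 = 90 diastolic. Three levels are therefore shown below.

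**3. How many people at baseline.** The quantity is 340 x P(24-hour mean at or above the level, and clinic <160 and <100 at both Visit 1 and Visit 2, given enrolment). The 340 is from the protocol and every other input is assumed:

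- paired clinic and ambulatory means of 140/88 with 133/82, 144/90 with 136.5/85, and 148/92 with 140/88;
- SD 12/9 or 13.6/9.7;
- clinic-ambulatory correlation 0.5 or 0.7, and systolic-diastolic correlation 0.6;
- between-visit correlation 0.75, with 0.85 as a sensitivity value;
- enrolment approximated as a 24-hour mean >=130 or >=80, to represent the white coat exclusion.

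Multivariate normal simulation gives:

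| 24-hour level | Affected, of 340 | Share |
|---|---|---|
| 160 systolic only | about 1-8 | 0.3-2.4% |
| 160 systolic or 100 diastolic | about 3-17 | 17/340 = 5% at the top |
| 150 systolic or 90 diastolic | about 50-87 | 50/340 = 15% to 87/340 = 26% |

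A cruder model, using systolic pressure only, one clinic reading and no diastolic alert, gives about 0-21 at 160, 3-81 at 150 and 17-133 at 145. The choice of level drives the answer.

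**4. How many people at 6 months.** With the planned 15% dropout, 340 x 0.85 = 289. For 160 systolic only, one clinic visit and no conditioning on enrolment, the count is about 1-8 if pressure has not fallen, 0-5 after an assumed 5/3 mmHg fall and 0-2 after 10/6. The other two levels were not simulated at 6 months.

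**5. Effect of a notice on the outcomes.** Only Visit 2 notices precede the 6-month outcome. Take the extreme one-sided case: half of the top baseline count is in usual care, each of those people falls an extra 10-15 mmHg (assumed), and nobody in the intervention arm does. The usual-care mean then shifts by (count/2)/170 x 10-15:

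- 160 systolic: 4/170 x 10-15 = 0.24-0.35 mmHg;
- 160/100: 8.5/170 x 10-15 = 0.50-0.75 mmHg;
- 150/90: 43.5/170 x 10-15 = 2.6-3.8 mmHg.

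The design difference in 6.1 is 6.3 mmHg systolic. Visit 4 notices cannot change the 6-month result. At 12 months the same extreme case for 160 systolic gives at most 4/144.5 x 10-15 = 0.28-0.42 mmHg, where 289/2 = 144.5.

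**6. The link to withdrawal.** Section 8.1.1 makes an abnormal diagnostic result an adverse event if, among other things, it "leads to additional treatment or to further diagnostic tests". Section 2.5.4 then says: "Any subject who experiences an adverse event or serious adverse event will be immediately withdrawn from the study". An alert that sends a participant to the provider could thus cost that participant's later outcomes. Visit 2 notices are less exposed, because under 8.3 a condition present at screening "will be considered as baseline and not reported as an AE".

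**The case against.** The best defence is that these are not people with an unsuspected finding. Section 4.3 excludes anyone unaware of their high blood pressure. Participants have their own provider, receive their clinic pressures and are told on the visit day to continue guideline care. Because a normal mean leads to exclusion and a letter, anyone enrolled through ambulatory monitoring can infer that theirs was not normal. The opening sentence of 2.5.1 could be read as a general promise to release relevant results. The row for Visit 4 is part of a visit-window table, so its silence is weak evidence that nobody looks at the recording. The appendix, which includes ambulatory instructions and a study calendar, was not supplied.

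Much of this stands, and it limits the harm. It does not supply a notice. Knowing that a mean is not normal is different from knowing that it is severe. The general promise is cut back by the restrictive list that follows it. The follow-up table is described as keyed to clinic values. The adverse-event rule in 8.1.1 is partly discretionary and directs no message to participant or provider. An appendix alert remains possible, which is why the point is confined to the supplied text.

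A reader might also infer that the baseline and 6-month means are merely delayed until month 12. The documents do not say so: 5.4.5 refers to final values, and no section says that the earlier means are shared at all.

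**Conclusion.** The point holds for the supplied text. The disclosure list is closed, its only ambulatory trigger is a normal mean at Visit 2, and no section states an action for a severely raised mean at Visit 2 or Visit 4 when clinic pressure is below 160/100.

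Its size is not known. The counts in steps 3 and 4 rest on assumed distributions and an assumed level. Counts are lower where a prior clinical recording or the automated office technique replaces the baseline study recording. A reader might conclude that the gap is minor and touches few people. That follows only if severe is set at about 160 systolic or 160/100, and the documents fix no such level. On the 10 mmHg offset implied by 3.1.2, up to about a quarter of the cohort could be in this position.

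Nor does the gap undermine the primary comparison, as a reader might infer. The missing trigger applies to both arms alike, and antihypertensive changes ("including medication initiation, discontinuation, and/or dose changes) are allowed throughout the study") are already part of the design. This is a safety omission that is cheap to close.

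**What to change.** - **2.5.1:** add to the list a severely raised mean 24-hour systolic or diastolic pressure at Visits 2 and 4. The study's medical lead should fix the level in advance; 160/100 is one choice that keeps alerts few. Apply it identically in both arms with the existing incidental finding form, and fax the form where the participant gave the provider's details.
- **5.4.3:** add review of the downloaded mean to the Visit 4 row, with notice on the day the recording is read.
- **2.5.4:** state that such a notice alone is not an adverse event requiring withdrawal, so that alerted participants keep their remaining outcomes.
- **Appendix:** if it already holds such an alert, cross-reference it in 2.5.1 instead.

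The cost is protocol and form wording plus a small amount of review work at Visit 4, where 5.4.1.2 describes upload of the recording without saying when it happens. At Visit 2 the mean is already read. The other downside is somewhat earlier treatment of alerted participants. Even in the extreme case of step 5 this is below 1 mmHg at 6 months for 160/100, but it becomes material at 150/90. The level should therefore be chosen with both safety and this effect in view.
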